# **8. PROJECT MANAGEMENT**

## **8.1. Project steering committee**

There will be a project steering committee led by the principal investigator and project coordinator to follow up all the project phases and to overcome possible problems. [name], [name], [name], [name] and [name] are responsible for study design, quality assurance and report writing. Local investigators and coordinators of data collection: [name].

## **8.2. Dissemination of results and publication policy**

The results of this study will be published in a peer-reviewed medical journal. We have no restrictions in publication of outcomes of this study.

## **8.3. Problems anticipated**

No significant problems are foreseen in this observational study.

## **8.4. Timeline of project**

Ethical Clearance: January-February 2019

Training of operators: February 2019

Data Collection and Data entry: March 2019

Data analysis: May-June 2019

Preliminary results: July 2019

Final report: September 2019

### **8.5. Amendments**

Amendments are changes made to the research protocol after a favorable opinion by the accredited ethical committee has been given. All amendments will be notified to the EC that gave a favorable opinion. Non-substantial amendments (typing errors and administrative changes) will not be notified to the accredited EC and the competent authority, but will be recorded and filed by the sponsor.

### **8.6. Temporary halt and (prematurely) end of study report**

In the unlikely event of a temporary halt or early stopping of the study, the investigator/sponsor will notify the accredited EC of the end of the study within a period of 8 weeks. The end of the study is defined as the last patient included. The investigators will notify the EC immediately of a temporary halt of the study, including the reason of such an action. In case the study is ended prematurely, the investigators will notify the accredited EC within 15 days, including the reasons for the premature termination. Within one year after the end of the study, the investigators will submit a final study report with the results of the study, including any publications/abstracts of the study, to the accredited EC.

## **9. ETHICS AND INFORMED CONSENT**

### **9.1. Regulation statement**

This study will be conducted according to the principles of the Declaration of Helsinki (revision Fortaleza, Brazil, October 2013). Approval to carry out this study will be sought from the relevant Review Board of Sierra Leone Ethics and Scientific Review Committee and from Doctors with Africa – CUAMM board of directors.

### **9.2. Recruitment and consent**

No ethical concern is attributable to this study due to its observational nature. No direct therapeutic intervention on patient is part of the study design. Personal information (name, age, community, etc.) from patient chart will be anonymized and no patients will be recognizable during the realization or dissemination phases of the study. Serial obstetrical ultrasound examinations are already standard of care in obstetric patients in PCMH and point of care ultrasound is also normally performed in emergency settings at the outpatient department of the hospital. The report of the expert ultrasound scan would be attached to the clinical chart, as already routine when an ultrasound is performed in the PCMH scanning room. For these reasons, and considering the medical urgency characterizing most inclusion criteria, a waiver of patient individual informed consent is kindly requested to this EC. Sharing of patient data will follow Good Clinical Practice guidelines and ethics review committee advice.

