### **3.4. Current challenges with obstetric diagnostics in PCMH**

Princess Christian Maternal Hospital (PCMH) is only the tertiary perinatal hospital in Freetown, Sierra Leone, which accommodates nearly 9000 admissions a year (11). More than 6000 deliveries a year are managed at the hospital, with more than one third of cases being major obstetrical emergencies including eclampsia and peripartum hemorrhages. Furthermore, the hospital accepts emergency referrals from 6 hospitals and 112 peripheral clinics in the Western region of the country. Major causes of maternal mortality at PCMH include postpartum and antepartum hemorrhage, eclampsia and infection (12).

In the 2017 Annual Report (12), it was shown that diagnoses made at admission by house doctors at outpatient department were frequently different from the final diagnoses made by the house officers specialized in obstetrics. For example, approximately 40% of the patients admitted to the hospital were initially diagnosed with anemia, but most of them were subsequently found to be in fatal conditions caused by placenta abruption (12). It is obvious that confirming a diagnosis is not the

only step needed to avoid mortality, but it is pivotal to establish a functional system to save critically ill patients. Lack of access to ultrasound in the delivery room often resulted in late diagnosis of malpresentation, breech presentation or multiple pregnancies. Intra-uterine fetal death (IUFD) was frequently observed but unnoticed until they were delivered by unnecessary cesarean sections.

At the emergency outpatient department of PCMH, clinical examinations and history taking are the only means to reach diagnoses, based on which subsequent management strategies are planned. Measurement of hemoglobin and lactate are the only modality available for in-house doctors to support their diagnosis. Ultrasound machine is intermittently available but the frequent low quality of the images acquired and the unstable electric supply of the hospital hampers repeatability and reliability of the ultrasound examinations.

Stethoscope or doppler devices are seldom available or functional. Traube's monaural stethoscope is the only the device available for the in-house doctors or midwives to listen to the fetal heart. Prompt diagnosis and treatment decisions are frequently required in the case of obstetric emergencies, in which delay in the recognition of the conditions of the fetus and mothers often resulted in demise of both.

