#### **5.1.Population**

##### **5.1.1.Inclusion criteria**

In order to be eligible to participate in the observational study, a patient must meet the following criteria:

- Admitted to the emergency department, outpatient department, in-patient department or antenatal care (ANC) of the PCMH during the study period.
- Fulfills one or more of the five inclusion categories defined in Table 1.
- (Verbal or written) informed consent of the patient or his/her formal representative, if required by ethical committee (decision is pending whether informed consent, either verbal or written, is required from individual patients).

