## **6.5.SAEs**

Because all proceedings in the method of this study are based on common clinical practice and ultrasound is a non-invasive procedure that cannot injure patients, there are no serious adverse events (SAEs) expected.

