#### **7.1.2.Data sharing**

Data derived from this study will be shared with the clinical team directly responsible for patient's care and with hospital leadership and management team for monitoring and/or audit purposes. **Specifically, a copy of the final expert report performed with the conventional apparatus will be attached to the patient's clinical chart to be visualized by the clinical team responsible for patient's care.** After publication of the primary results, on request the pooled dataset will be available for secondary analysis, after judgment and approval of scientific quality and validity of the proposed analysis by the steering committee.

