### **9.3. Benefits and risks assessment**

Because all proceedings in the method of this study are based on common clinical practice and ultrasound is a non-invasive procedure that cannot injure patients, the risk of this study is considered very low. The ultrasound performed for this study are not charged to the patient or to the hospital administration.

As this study aims at assessing the reliability of obstetric findings, we cannot choose another patient population. Patients included in this study may benefit in terms of systematic ultrasound monitoring in a setting where obstetric imaging modalities are still hampered by technical and non-technical difficulties.

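### No maximum interval is set between the hand-held scan and the expert reference scan, and no scan times are listed for collection; a minor point is that one ground for the consent waiver (9.2) conflicts with 3.4.

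*Protocol*

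**What the plan says.** **Timing of the two scans.** Under 6.3.2 the medical officer does the hand-held scan as soon as the woman is admitted as an emergency, or where she is seen in ANC or on the ward. An expert then repeats the examination on a standard machine in the scanner room. No time is attached to the repeat. The expert result is the reference for the primary endpoint, the accuracy averaged over findings (6.1.1). The list in 6.1.3 covers the findings, demographics, admission type, and date and outcome at discharge.

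**Conditions on site.** Section 3.4 says of ultrasound at the hospital: "Ultrasound machine is intermittently available but the frequent low quality of the images acquired and the unstable electric supply of the hospital", and names these as what undermines repeatable scanning. Section 5.1.2 excludes women in whom ultrasound is not feasible, with power failure and absent sonographers as examples. It does not say which of the two scans it means. Section 6.4.1 allows withdrawal for urgent medical reasons.

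**Consent.** Section 9.2 says "point of care ultrasound is also normally performed in emergency settings at the outpatient department of the hospital" and, on this and other grounds, "a waiver of patient individual informed consent is kindly requested to this EC". Section 5.1.1 records that the "decision is pending whether informed consent, either verbal or written, is required from individual patients". Section 3.4 says: "At the emergency outpatient department of PCMH, clinical examinations and history taking are the only means to reach diagnoses". Sections 6.5 and 9.3 rest low risk on the statement that "all proceedings in the method of this study are based on common clinical practice and ultrasound is a non-invasive procedure that cannot injure patients".

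**The concern.** An accuracy study assumes that the reference scan shows the same state that the index operator saw. Four of the five inclusion categories are acute or evolving conditions: early bleeding, pre-eclampsia, antepartum haemorrhage and prolonged labour. Fetal heart activity, presentation, amniotic fluid, free fluid and retroplacental haematoma can all change while a woman waits for the scanner room. A hand-held reading that was right when made is then scored as wrong. With no limit on the gap, no listed scan times and unstable power, such pairs could be neither prevented nor identified afterwards. A statistical analysis plan cannot supply times that were not recorded.

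The waiver text is a separate and smaller matter. The ethics committee is asked to decide on a description of usual care that differs from the one in the background section.

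**Working it through.** **1. Search for a time limit.**

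| Section | On timing |
|---|---|
| 1 | Hand-held scan at admission, or later if clinically indicated; no gap to the expert scan |
| 3.5 | Where and by whom the reference is done; no time |
| 5.3 | Two months of enrolment, outcome at discharge; no gap |
| 6.1.3 | No scan times, no intervening treatment or delivery |
| 6.1.4 | Mutual blinding; no timing |
| 6.3.2 | Hand-held scan at once; expert repeat untimed |
| 7.2, 7.3 | No rule for a late reference scan |

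**2. Readings exposed.** Section 5.2 expects 15 women per category for each of 4 operators: 15 × 4 = 60 per category. I count each woman in one category. Table 2 has 3 + 4 + 4 + 4 + 6 = 21 findings over the five categories, so 21 × 60 = 1,260 paired readings. Outside ANC there are 15 × 60 = 900 (71%).

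Of these, the five findings named above appear 2 times in early bleeding (fetal heart, free fluid), 3 in pre-eclampsia (fetal heart, fluid pocket, presentation), 3 in antepartum haemorrhage (fetal heart, haematoma, fluid pocket) and 3 in prolonged labour (fetal heart, presentation, fluid pocket). That is 11 × 60 = 660 readings, or 52% of 1,260. If intrauterine pregnancy is also treated as changeable, it is 12 × 60 = 720 (57%). Which findings can change within hours is a clinical judgement of mine and is not stated in the protocol.

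**3. Effect on accuracy.** Let a be the accuracy if both scans saw the same state, and c the share of pairs in which the state changes. With dichotomous findings and change independent of hand-held error:

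observed accuracy = a(1 − c) + (1 − a)c = a − c(2a − 1).

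| c (of all pairs) | a = 95% | a = 90% |
|---|---|---|
| 1% | 94.1% | 89.2% |
| 3% | 92.3% | 87.6% |
| 5% | 90.5% | 86.0% |

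Example: 0.95 − 0.05 × (2 × 0.95 − 1) = 0.95 − 0.045 = 0.905. Without independence the fall still cannot exceed c, which is the case in which every changed pair had been read correctly. If the endpoint is an unweighted mean over findings with a common a, c is the mean change share over findings.

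**4. What these values of c require.** If only the 660 readings can change, c = 1%, 3% and 5% of all pairs means change in 0.01 × 1,260/660 = 1.9%, 5.7% and 9.5% of them. With 720 changeable readings it is 1.8%, 5.3% and 8.8%. The protocol gives no change rate to set beside these.

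**5. Section 9.2 beside 3.4.** Both describe emergency care at the outpatient department of the same hospital. One calls bedside ultrasound normal practice there. The other says that history and examination are all there is, supported by haemoglobin and lactate, with a machine available only at times. Intermittent access with poor images is not normal performance. Section 9.3 also presents scarcity as a benefit of joining: "Patients included in this study may benefit in terms of systematic ultrasound monitoring in a setting where obstetric imaging modalities are still hampered".

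**The case against.** **The size is assumed.** The documents contain no change rate, and the upper rows need nearly one changeable reading in ten to alter between scans. In practice the expert scan may follow within the hour, and the effect would then be negligible. This stands: the table is an illustration and not a forecast.

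**Many changes would not be mis-scored.** A woman who delivers before the expert scan is a lost pair and not a false hand-held error. That is correct, and it is a reason to record delivery separately.

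**The CRF or operating procedure may hold the times.** Neither is at hand, so they may. A recorded time would allow late pairs to be identified, but it is not a limit.

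**The waiver sentences can be reconciled.** Section 3.4 itself mentions ultrasound examinations, so its claim that there is nothing else is loose, and 9.2 may mean usual practice when the machine works. This softens the conflict without removing it. The other statement in 9.2, that serial scans are standard of care, is not contradicted by the outpatient sentence.

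**Three stronger readings** might be inferred, and none is supported:

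- *Lost pairs bias sensitivity and specificity.* They do so only if loss depends on the hand-held result. Loss through power failure or an absent sonographer need not, and the reference operator is blinded to that result (6.1.4).
- *The hand-held reading reaches the treating team.* The opening of 7.1.2, "Data derived from this study will be shared with the clinical team directly responsible for" the patient, could suggest it. The next sentence specifies the expert report, and 9.2 repeats this, so the point is largely settled.
- *The waiver fails.* It also rests on the observational design, anonymisation, routine charting of the expert report and urgency.

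**Conclusion.** The main point holds. As written, the protocol lets the reference scan follow the hand-held scan at any distance and lists nothing from which the distance could be reconstructed. Under independence and a above 50%, the error runs against the device. At an assumed 95% true accuracy, the observed figure would be 94.1% to 90.5% for change in 1% to 5% of all pairs. Both a and c are assumptions, and the design gap does not depend on them. It should be closed before enrolment, because missing times cannot reliably be recovered later.

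The documents do not show that accuracy will in fact be materially understated.

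The conflict between 9.2 and 3.4 is real. It touches one of several grounds for the waiver, changes no result, and needs only a wording correction.

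**What to change.** 1. **6.3.2:** set a feasible maximum interval from hand-held to expert scan, the same whatever the hand-held result. Choose it from a short pilot of the bedside-to-scanner delay, for example in training week 2, when the hand-held device is taught. Practice in the scanning room in week 1 cannot show that delay.
2. **6.1.3:** list both scan times and any treatment or delivery between them.
3. **5.1.2:** apply the feasibility exclusion before the hand-held scan. Report the number of women without a reference scan by hand-held result, so that a reader can see whether loss depends on it.
4. **Analysis:** report accuracy with and without pairs outside the interval, here or in the analysis plan.
5. **9.2 or 3.4:** correct whichever is untrue before the committee decides on the waiver.

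The cost is about three CRF fields (fewer if the times are already there), a few reworded sentences, and some pairs falling outside the interval when power fails.

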### **9.3. Benefits and risks assessment**

Because all proceedings in the method of this study are based on common clinical practice and ultrasound is a non-invasive procedure that cannot injure patients, the risk of this study is considered very low. The ultrasound performed for this study are not charged to the patient or to the hospital administration.

As this study aims at assessing the reliability of obstetric findings, we cannot choose another patient population. Patients included in this study may benefit in terms of systematic ultrasound monitoring in a setting where obstetric imaging modalities are still hampered by technical and non-technical difficulties.

### **10. BUDGET AND OTHER SUPPORT FOR THE PROJECT**

Funding is actively being sought. However if funding is not obtained the following resources will be utilized. Investigators time will be given voluntarily. Doctors with Africa – CUAMM, will fund ethical committee fees. Waiver for costs for publication based on low-income country status will be sought from the relevant international journals.

# 12. APPENDIX

## Ultrasound probe to be used in this study

### Specification for Ultrasound Probe “US-304”

Ver 2.0.1  
July 25th, 2018

#### 1. General Description

[figure not shown]
This device allows you to receive the high-resolution ultrasound images by utilizing the power from a general purposed laptop/tablet.

#### 2. System

##### 2.1 Operation

The probe on this device is installed with ultrasound frequency sender and receiver, amplifier and ADC circuit which send ultrasound image data as USB signals. The signal gets processed through PC viewer software to be projected as image on the screen. This device also has scanning, mode control, and measuring functions. In addition, this device has recording-functions for tomographic images and results of measurement and connecting-functions for sending images and transferring data to outside network.

##### 2.2 Diagram

##### 2.3 Model Picture

1

#### 3. Functional Specification for Abdomen

3.1 Device	
Size	W 85 x L 180 x Thickness 18 mm (Main body only)
Weight	167 g (cable included)
Cable Length	1.5 m
3.2 Oscillator	
Configuration	Convex (Curved array)
Curvature	Radius 60mm
View Angle	60 degree
Element Count	64 Elements
Element Pitch	1.0 mm
Element Width	12 mm
Acoustic Matching Layer	1 Layer
Lens Focal Point	100 mm
3.3 Function	
Sending Frequency	2.5 - 4.0MHz
Display Mode	B, B/B, BM
Measurement	Distance, Area, Circumference
Special Measurement	Obstetrics Measurement
Convertible	Convertible
Sync View*	*A function to synchronously record ultrasound images for the internal body and camera images for the external body

#### 4. Display Device

4.1 Recommended Device	Panasonic ToughPad FZ-G1 Series
4.2 OS	Windows 8.1 Windows 10
4.3 CPU	Intel Core i3 (CLK 2GHz and above) AMD A4 (CLK 2GHz and above)
4.4 RAM	4GB and above

2

#### 5. Power Source

5.1 Outlet	5V Max. 350mA USB Power Source
5.2 Operational Duration	Estimated 120 minutes when the battery is fully charged

#### 6. Circuit Configuration

6.1 Sending	
Excitation Element Number	8 Elements
Excitation Voltage	±48V and above
Sending Pulse	1.5 Wave Length Square Wave
Focus	Single / fixed
6.2 Receiving	
Number of Receiving Circuit	A similar processing output to 16 sensor elements, using an 8 sensors circuit twice.
Focus	Dynamic Focus

#### 7. Image Processing

7.1 Line interpolation	
7.2 Frame correlation	

#### 8. Estimated lifetime with appropriate use

7 years

The device “US-304” can be connected to the smartphone which fulfills certain requirements. Any smartphone run by Android OS can be used for the portable ultrasound device after the application developed by the same manufacture to run the program for ultrasound examination is installed. Once the application is installed in the smartphone, it will be an interface to control the device to optimize the images acquired by ultrasound examinations and to perform obstetric calculations for estimation of gestational ages based on the measurements of bi-parietal diameter (BPD) or femur length (FL). In the study, the ultrasound device (probe type: convex type with 3.5 MHz) and a smartphone (ASUS; Taiwan), in which the application has already been installed, will be provided for practical training sessions.

The manufacture information is given below:

Lequio Power Technology Corp.

[name]

[contact] [contact]
